#### **7.2.4 Definition of an Overdose for This Protocol and Reporting of Overdose to the Sponsor and to Merck**

For purposes of this trial, an overdose of pembrolizumab will be defined as any dose of 1,000 mg or greater ( $\geq$ 5 times the indicated dose). No specific information is available on the treatment of overdose

**Product:** Pembrolizumab

**Protocol/Amendment No.:** UVA Breast 48

V04-13-21

of pembrolizumab. Appropriate supportive treatment should be provided if clinically indicated. In the event of overdose, the subject should be observed closely for signs of toxicity. Appropriate supportive treatment should be provided if clinically indicated.

If an adverse event(s) is associated with (“results from”) the overdose of a Merck product, the adverse event(s) is reported as a serious adverse event, even if no other seriousness criteria are met.

If a dose of Merck’s product meeting the protocol definition of overdose is taken without any associated clinical symptoms or abnormal laboratory results, the overdose is reported as a non-serious Event of Clinical Interest (ECI), using the terminology “accidental or intentional overdose without adverse effect.”

All reports of overdose with and without an adverse event must be reported within 24 hours to the Sponsor and within 2 working days hours to Merck Global Safety. (Attn: Worldwide Product Safety; [contact])

### **7.2.5 Reporting of Pregnancy and Lactation to the Sponsor and to Merck**

Although pregnancy and lactation are not considered adverse events, it is the responsibility of investigators or their designees to report any pregnancy or lactation in a subject (spontaneously reported to them) that occurs during the trial.

Pregnancies and lactations that occur after the consent form is signed but before treatment allocation/randomization must be reported by the investigator if they cause the subject to be excluded from the trial, or are the result of a protocol-specified intervention, including but not limited to washout or discontinuation of usual therapy, diet, placebo treatment or a procedure.

Pregnancies and lactations that occur from the time of treatment allocation/randomization through 120 days following cessation of Sponsor’s product, or 30 days following cessation of treatment if the subject initiates new anticancer therapy, whichever is earlier, must be reported by the investigator. All reported pregnancies must be followed to the completion/termination of the pregnancy. Pregnancy outcomes of spontaneous abortion, missed abortion, benign hydatidiform mole, blighted ovum, fetal death, intrauterine death, miscarriage and stillbirth must be reported as serious events (Important Medical Events). If the pregnancy continues to term, the outcome (health of infant) must also be reported.

Such events must be reported within 24 hours to the Sponsor and within 2 working days to Merck Global Safety. (Attn: Worldwide Product Safety; [contact])

### **7.2.6 Immediate Reporting of Adverse Events to the Sponsor and to Merck**

For the time period beginning when the consent form is signed until treatment allocation/randomization, any serious adverse event, or follow up to a serious adverse event, including death due to any cause other than progression of the cancer under study that occurs to any subject must be reported within 24 hours to the Sponsor and within 2 working days to Merck Global Safety if it causes the subject to be excluded from the trial, or is the result of a protocol-specified intervention, including but not limited to washout or discontinuation of usual therapy, diet, placebo treatment or a procedure.

For the time period beginning at treatment allocation/randomization through 90 days following cessation of treatment, or 30 days following cessation of treatment if the subject initiates new anticancer therapy, whichever is earlier, any serious adverse event, or follow up to a serious adverse event, including death due to any cause other than progression of the cancer under study whether or not related

**Product:** Pembrolizumab

**Protocol/Amendment No.:** UVA Breast 48

V04-13-21

to the Merck product, must be reported within 24 hours to the Sponsor and within 2 working days to Merck Global Safety.

Additionally, any serious adverse event, considered by an investigator who is a qualified physician to be related to Merck product that is brought to the attention of the investigator at any time following consent through the end of the specified safety follow-up period specified in the paragraph above, or at any time outside of the time period specified in the previous paragraph also must be reported immediately to the Sponsor and to Merck Global Safety.

All subjects with serious adverse events must be followed up for outcome.

**SAE reports and any other relevant safety information are to be forwarded to the Merck Global Safety [contact]**

A copy of all 15 Day Reports and Annual Progress Reports is submitted as required by FDA, European Union (EU), Pharmaceutical and Medical Devices agency (PMDA) or other local regulators. Investigators will cross reference this submission according to local regulations to the Merck Investigational Compound Number (IND, CSA, etc.) at the time of submission. Additionally investigators will submit a copy of these reports to Merck & Co., Inc. (Attn: Worldwide Product Safety; [contact]) at the time of submission to FDA.

#### **7.2.6.1 Events of Clinical Interest**

Selected non-serious and serious adverse events are also known as Events of Clinical Interest (ECI) and must be reported within 24 hours to the Sponsor and within 2 working days to Merck Global Safety. (Attn: Worldwide Product Safety; [contact]).

For the time period beginning when the consent form is signed until treatment allocation/randomization, any ECI, or follow up to an ECI, that occurs to any subject must be reported within 24 hours to the Sponsor and within 2 working days to Merck Global Safety if it causes the subject to be excluded from the trial, or is the result of a protocol-specified intervention, including but not limited to washout or discontinuation of usual therapy, diet, placebo treatment or a procedure.

For the time period beginning at treatment allocation/randomization through 90 days following cessation of treatment, or 30 days following cessation of treatment if the subject initiates new anticancer therapy, whichever is earlier, any ECI, or follow up to an ECI, whether or not related to Merck product, must be reported within 24 hours to the Sponsor and within 24 hours to Merck Global Safety.

Events of clinical interest for this trial include:

1. an overdose of Merck product, as defined in [Section 7.2.3](#) - Definition of an Overdose for This Protocol and Reporting of Overdose to the Sponsor, that is not associated with clinical symptoms or abnormal laboratory results.
2. an elevated AST or ALT lab value that is greater than or equal to 3X the upper limit of normal and an elevated total bilirubin lab value that is greater than or equal to 2X the upper limit of normal and, at the same time, an alkaline phosphatase lab value that is less than 2X the upper limit of normal, as determined by way of protocol-specified laboratory testing or unscheduled laboratory testing.\*

**\*Note:** These criteria are based upon available regulatory guidance documents. The purpose of the criteria is to specify a threshold of abnormal hepatic tests that may require an additional evaluation for an underlying etiology.

**Product:** Pembrolizumab

**Protocol/Amendment No.:** UVA Breast 48

V04-13-21

#### **7.2.6.2 Protocol-Specific Exceptions to Serious Adverse Event Reporting**

Efficacy endpoints as outlined in this section will not be reported to Merck as described in [Section 7.2.6](#).- Immediate Reporting of Adverse Events to the Sponsor and to Merck, unless there is evidence suggesting a causal relationship between the drug and the event. Any such event will be submitted to the Sponsor within 24 hours and to Merck Global Safety within 2 working days either by electronic or paper media.

Specifically, the suspected/actual events covered in this exception include any event that is disease progression of the cancer under study.

The Sponsor will monitor unblinded aggregated efficacy endpoint events and safety data to ensure the safety of the subjects in the trial. Any suspected endpoint which upon review is not progression of the cancer under study will be forwarded to Merck Global Safety as a SAE within 2 working days of determination that the event is not progression of the cancer under study

Hospitalization related to convenience (e.g.transportation issues etc.) will not be considered a SAE.

#### **7.2.7 Evaluating Adverse Events**

An investigator who is a qualified physician will evaluate all adverse events according to the NCI Common Terminology for Adverse Events (CTCAE), version 4.0. Any adverse event which changes CTCAE grade over the course of a given episode will have each change of grade recorded on the adverse event case report forms/worksheets.

All adverse events regardless of CTCAE grade must also be evaluated for seriousness.

**Product:** Pembrolizumab

**Protocol/Amendment No.:** UVA Breast 48

V04-13-21

**Table 7: Evaluating Adverse Events**

An investigator who is a qualified physician, will evaluate all adverse events as to:

V4.0 CTCAE Grading	Grade 1	Mild; asymptomatic or mild symptoms; clinical or diagnostic observations only; intervention not indicated.
	Grade 2	Moderate; minimal, local or noninvasive intervention indicated; limiting age-appropriate instrumental ADL.
	Grade 3	Severe or medically significant but not immediately life-threatening; hospitalization or prolongation of hospitalization indicated; disabling; limiting self-care ADL.
	Grade 4	Life threatening consequences; urgent intervention indicated.
	Grade 5	Death related to AE
Seriousness	A serious adverse event is any adverse event occurring at any dose or during any use of Merck product that:	
	† Results in death; or	
	† Is life threatening; or places the subject, in the view of the investigator, at immediate risk of death from the event as it occurred (Note: This does not include an adverse event that, had it occurred in a more severe form, might have caused death.); or	
	† Results in a persistent or significant disability/incapacity (substantial disruption of one's ability to conduct normal life functions); or	
	† Results in or prolongs an existing inpatient hospitalization (hospitalization is defined as an inpatient admission, regardless of length of stay, even if the hospitalization is a precautionary measure for continued observation. (Note: Hospitalization for an elective procedure to treat a pre-existing condition that has not worsened is not a serious adverse event. A pre-existing condition is a clinical condition that is diagnosed prior to the use of a Merck product and is documented in the patient's medical history.); or	
	† Is a congenital anomaly/birth defect (in offspring of subject taking the product regardless of time to diagnosis); or	
	Is a new cancer (that is not a condition of the study) (although not serious per ICH definition, is reportable to the Sponsor within 24 hours and to Merck within 2 working days to meet certain local requirements); or	
	Is an overdose (whether accidental or intentional). Any adverse event associated with an overdose is considered a serious adverse event for collection purposes. An overdose that is not associated with an adverse event is considered a non-serious event of clinical interest and must be reported within 24 hours to the Sponsor and to Merck within 2 working days..	

**Product:** Pembrolizumab

**Protocol/Amendment No.:** UVA Breast 48

V04-13-21

	
Other important medical events that may not result in death, not be life threatening, or not require hospitalization may be considered a serious adverse event when, based upon appropriate medical judgment, the event may jeopardize the subject and may require medical or surgical intervention to prevent one of the outcomes listed previously (designated above by a †).
						
Duration	Record the start and stop dates of the adverse event. If less than 1 day, indicate the appropriate length of time and units						
Action taken	Did the adverse event cause Merck product to be discontinued?						
Relationship to Merck Product	
Did Merck product cause the adverse event? The determination of the likelihood that Merck product caused the adverse event will be provided by an investigator who is a qualified physician. The investigator's signed/dated initials on the source document or worksheet that supports the causality noted on the AE form, ensures that a medically qualified assessment of causality was done. This initialed document must be retained for the required regulatory time frame. The criteria below are intended as reference guidelines to assist the investigator in assessing the likelihood of a relationship between the test drug and the adverse event based upon the available information.
 
The following components are to be used to assess the relationship between Merck product and the AE; the greater the correlation with the components and their respective elements (in number and/or intensity), the more likely Merck product caused the adverse event (AE):
 

Exposure	Is there evidence that the subject was actually exposed to Merck product such as: reliable history, acceptable compliance assessment (pill count, diary, etc.), expected pharmacologic effect, or measurement of drug/metabolite in bodily specimen?	

Time Course	Did the AE follow in a reasonable temporal sequence from administration of Merck product? Is the time of onset of the AE compatible with a drug-induced effect (applies to trials with investigational medicinal product)?	

Likely Cause	Is the AE not reasonably explained by another etiology such as underlying disease, other drug(s)/vaccine(s), or other host or environmental factors	

	Exposure	Is there evidence that the subject was actually exposed to Merck product such as: reliable history, acceptable compliance assessment (pill count, diary, etc.), expected pharmacologic effect, or measurement of drug/metabolite in bodily specimen?	Time Course	Did the AE follow in a reasonable temporal sequence from administration of Merck product? Is the time of onset of the AE compatible with a drug-induced effect (applies to trials with investigational medicinal product)?	Likely Cause	Is the AE not reasonably explained by another etiology such as underlying disease, other drug(s)/vaccine(s), or other host or environmental factors
Exposure	Is there evidence that the subject was actually exposed to Merck product such as: reliable history, acceptable compliance assessment (pill count, diary, etc.), expected pharmacologic effect, or measurement of drug/metabolite in bodily specimen?						
Time Course	Did the AE follow in a reasonable temporal sequence from administration of Merck product? Is the time of onset of the AE compatible with a drug-induced effect (applies to trials with investigational medicinal product)?						
Likely Cause	Is the AE not reasonably explained by another etiology such as underlying disease, other drug(s)/vaccine(s), or other host or environmental factors						

**Product:** Pembrolizumab

**Protocol/Amendment No.:** UVA Breast 48

V04-13-21

Relationship to Merck Product (continued)	The following components are to be used to assess the relationship between the test drug and the AE: (continued)	
	Dechallenge	
Was Merck product discontinued or dose/exposure/frequency reduced?
 
If yes, did the AE resolve or improve?
 
If yes, this is a positive dechallenge. If no, this is a negative dechallenge.
 
(Note: This criterion is not applicable if: (1) the AE resulted in death or permanent disability; (2) the AE resolved/improved despite continuation of the Sponsor's product; or (3) the trial is a single-dose drug trial); or (4) Sponsor's product(s) is/are only used one time.)

	Rechallenge	
Was the subject re-exposed to Merck product in this study?
 
If yes, did the AE recur or worsen?
 
If yes, this is a positive rechallenge. If no, this is a negative rechallenge.
 
(Note: This criterion is not applicable if: (1) the initial AE resulted in death or permanent disability, or (2) the trial is a single-dose drug trial); or (3) Sponsor's product(s) is/are used only one time).
 
NOTE: IF A RECHALLENGE IS PLANNED FOR AN ADVERSE EVENT WHICH WAS SERIOUS AND WHICH MAY HAVE BEEN CAUSED BY MERCK PRODUCT, OR IF REEXPOSURE TO MERCK PRODUCT POSES ADDITIONAL POTENTIAL SIGNIFICANT RISK TO THE SUBJECT, THEN THE RECHALLENGE MUST BE APPROVED IN ADVANCE BY THE SPONSOR AS PER DOSE MODIFICATION GUIDELINES IN THE PROTOCOL.

	Consistency with Trial Treatment Profile	Is the clinical/pathological presentation of the AE consistent with previous knowledge regarding Merck product or drug class pharmacology or toxicology?
The assessment of relationship will be reported on the case report forms /worksheets by an investigator who is a qualified physician according to his/her best clinical judgment, including consideration of the above elements.		
Record one of the following	Use the following scale of criteria as guidance (not all criteria must be present to be indicative of Merck product relationship).	
Yes, there is a reasonable possibility of Merck product relationship.	There is evidence of exposure to Merck product. The temporal sequence of the AE onset relative to the administration of Merck product is reasonable. The AE is more likely explained by Merck product than by another cause.	
No, there is not a reasonable possibility of Merck product relationship	Subject did not receive the Merck product OR temporal sequence of the AE onset relative to administration of Merck product is not reasonable OR the AE is more likely explained by another cause than the Merck product. (Also entered for a subject with overdose without an associated AE.)	

**Product:** Pembrolizumab

**Protocol/Amendment No.:** UVA Breast 48

V04-13-21

### 7.2.8 Adverse Event Classifications

Adverse events (AEs) are classified into sections, specified in the CTCAE v4.03. For specific classifications pertaining to the protocol, we specify the following:

Hematologic/Metabolic- Any AE coded under one of the following CTCAE v4.03 categories should be reported under the Hematologic/Metabolic adverse event classification:

Table 8: Hematologic/Metabolic Classifications

Section	AE
Blood and lymphatic	Anemia Leukocytosis
Investigations	ALL EXCEPT: Carbon monoxide diffusing capacity decreased Ejection fraction decreased Forced expiratory volume decreased Vital capacity abnormal Weight gain Weight loss
Metabolism and nutrition disorders	ALL EXCEPT: Alcohol intolerance Anorexia Dehydration Glucose intolerance Iron overload Obesity Tumor lysis syndrome

Non-hematologic/Non-Metabolic- Any AE not reported under hematologic/metabolic, ocular, or allergic/autoimmune, should be reported under the non-hematologic/non-metabolic adverse event classification.

Allergic/Autoimmune – Only AEs coded as Immune System Disorder: Allergic reaction, autoimmune disorder, or anaphylaxis should be reported under the Allergic/Autoimmune adverse event classification. Other AEs coded under Immune System Disorder should be reported under Non-hematologic/Non-metabolic.

### 7.2.9 Agent-Specific Expected Adverse Events List

#### 7.2.9.1 Pembrolizumab

Treatment-related adverse reactions are described in Section 7 of the Investigator's Brochure.

**Product:** Pembrolizumab

**Protocol/Amendment No.:** UVA Breast 48

V04-13-21

### **7.2.9.2 Adverse Effects Considered Expected for HIFU**

Data for potential adverse effects related to the HIFU treatment are described in the Echopulse User's Manual.

### **7.2.9.3 Adverse events expected from biopsies**

#### **Adverse events expected from biopsies (highest grade expected—Grade 2)**

- Bleeding
- Bruising
- Pain
- Lymphedema
- Delayed wound healing
- Scarring
- Numbness
- Gross hematuria and/or dysuria and urinary frequency (prostate biopsies)
- hematochezia (prostate biopsies)
- Infection

### **7.2.10 Dose Limiting Toxicities**

A DLT of pembrolizumab is defined as an unacceptable, drug-related toxicity requiring permanent discontinuation, per [Table 4](#) (Dose Modification Guidelines for Drug-Related Adverse Events).

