## 2.0 TRIAL DESIGN

### 2.1 Trial Design

This is a two-arm pilot study of High-Intensity Focused Ultrasound (HIFU) and immunotherapy. The goals of the study are to obtain preliminary data on the safety of HIFU with immunotherapy, delivered concurrently, and to obtain preliminary estimates of change in T-cell frequency and activation for HIFU alone (day 15-21 of ARM A) and pembrolizumab and HIFU given in combination (day 15-21 of arm B). The central hypothesis is that focused energy induced immunogenic cell death will overcome limitations in antigen availability, and effective T-cell responses, and thereby enhance immune-therapy of advanced breast cancer. Our secondary hypothesis is that concomitant immune-activation will further augment CD8+ T-cell responses to tumor antigen released by HIFU. We will obtain preliminary data on whether HIFU promotes the presence of CD8+ T-cells in ablated primary tumors, blood and non-ablated distant metastases. Additional correlative science endpoints will be tested as exploratory endpoints.

[figure not shown]
Eligible subjects will be randomized 1:1 to the investigational treatments (Arm A) or (Arm B). Subjects on both arms will undergo HIFU treatment on day 15. Subjects randomized to Arm A will receive pembrolizumab administered IV every 3 weeks on days 22, 43, and 64. Subjects randomized to Arm B will receive pembrolizumab administered IV every 3 weeks on days 1, 22, 43 and 64. In all subjects, restaging breast cancer-dedicated chest, abdomen and pelvic CT scan will be performed at baseline and cycle 4. Biopsies of tumors treated with HIFU will be completed on all patients at days 1 and 22 with optional distant tumor site biopsies and additional biopsies of the HIFU treated breast lesion to be completed at day 64. The tissue removed at the biopsies will be evaluated as part of the immunologic correlative studies.

**Product:** Pembrolizumab

**Protocol/Amendment No.:** UVA Breast 48

V04-13-21

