#### **4.4 Rationale for Endpoints**

This study is designed primarily to test whether interfering with immune suppression by blocking the molecular interaction between the PD-1 receptor and its cognate ligand, PD-L1, increases the number and activation of TILs that are induced by the local ablative therapy.

The study is also designed to examine the safety of HIFU and pembrolizumab. HIFU therapy for breast lesions and breast cancer is generally well tolerated. Based on our experience at UVA (n=20) there has been no evidence of grade 4 toxicities in patients who received HIFU. Pembrolizumab has been studied in numerous clinical trials to date and was found to be well tolerated with no dose-limiting toxicities at the standard dose of 200 mg (see Investigator's Brochure). Our proposed study is the first study to combine HIFU and pembrolizumab in humans and safety is our secondary endpoint.

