**Note: Non-irAE will be managed as appropriate, following clinical practice recommendations.**

a AST/ALT: >3.0 to 5.0 x ULN if baseline normal; >3.0 to 5.0 x baseline, if baseline abnormal; bilirubin:>1.5 to 3.0 x ULN if baseline normal; >1.5 to 3.0 x baseline if baseline abnormal

b AST/ALT: >5.0 to 20.0 x ULN, if baseline normal; >5.0 to 20.0 x baseline, if baseline abnormal; bilirubin:>3.0 to 10.0 x ULN if baseline normal; >3.0 to 10.0 x baseline if baseline abnormal

c AST/ALT: >20.0 x ULN, if baseline normal; >20.0 x baseline, if baseline abnormal; bilirubin: >10.0 x ULN if baseline normal; >10.0 x baseline if baseline abnormal

d The decision to withhold or permanently discontinue pembrolizumab is at the discretion of the investigator or treating physician. If control achieved or  $\leq$  Grade 2, pembrolizumab may be resumed.

e Events that require discontinuation include, but are not limited to: encephalitis and other clinically important irAEs (eg, vasculitis and sclerosing cholangitis).

Dosing interruptions are permitted in the case of medical / surgical events or logistical reasons not related to study therapy (e.g., elective surgery, unrelated medical events, patient vacation, and/or holidays). Subjects should be placed back on study therapy within 3 weeks of the scheduled interruption, unless otherwise discussed with the Sponsor. The reason for interruption should be documented in the patient's study record

Note: There is no dose modification for HIFU as it is only administered once in this protocol.

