## **5.10 Clinical Criteria for Early Trial Termination**

Early trial termination will be the result of the criteria specified below:

- Quality or quantity of data recording is inaccurate or incomplete
- Poor adherence to protocol and regulatory requirements
- Incidence or severity of adverse drug reaction in this or other studies indicates a potential health hazard to subjects
- Plans to modify or discontinue the development of the study drug

In the event of Merck decision to no longer supply study drug, ample notification will be provided so that appropriate adjustments to subject treatment can be made.

**Product:** Pembrolizumab

**Protocol/Amendment No.:** UVA Breast 48

V04-13-21

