## **8.0 STATISTICAL ANALYSIS PLAN**

### **8.1 Statistical Analysis Plan Summary**

This is a pilot study of high intensity focused ultrasound (HIFU) and pembrolizumab, and is proposed as a pilot two-arm design. All patients will receive the FDA approved dosing of pembrolizumab and allocation to arms is randomized. Participants from arm A will first receive HIFU ablation and then a pembrolizumab infusion 1 week after an ablative procedure. Participants from arm B will first receive pembrolizumab at baseline and then undergo the HIFU ablation two weeks later. The goal is to obtain preliminary data on the safety of HIFU and pembrolizumab and to obtain estimates of change in immune parameters (proportion of activated CD8 tumor infiltrating lymphocytes (TILs) is primary) pre- and post-treatment. The trial will not be powered for cross arm comparison, but will nevertheless provide useful pilot data for the design of a larger trial of combined therapies.

Safety stopping rules will be employed within each study arm and will be judged by dose limiting toxicities (DLTs), defined in [Section 7.2.10](#). The primary objectives include assessing adverse events

**Product:** Pembrolizumab

**Protocol/Amendment No.:** UVA Breast 48

V04-13-21

and change in the proportion of CD8+ to CD4+ tumor infiltrating lymphocytes (TILs) in the primary ablation zone. Secondary endpoints include assessing change in CD8+ T-cell responses at peri-ablation zones, clinical responses at local and distant metastatic sites, disease free survival (DFS), and overall survival (OS). Exploratory endpoints include assessing change in T-cells in peripheral blood, markers of T-cell activation, gene expression profiling, and enumeration of myeloid derived suppressor cells.

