## 8.2 Statistical Analysis Plan

Target sample size is 12 participants, which was chosen as a feasible number that could be accrued within a 2 year accrual period. Participants will be randomized 1:1 to treatment arms A and B with block randomization using blocks of size 2 or 4. Participants are considered evaluable if they satisfy all inclusion and exclusion criteria and have adequate endpoint measurements during respective cohort timelines. Adjusting for a 10% unevaluable/drop-out rate, maximum target accrual is estimated at 15 participants.

The purpose is to assess the adverse events profile of pembrolizumab and focused ultrasound therapy and estimate the difference in the TILs at baseline and 3 weeks within each arm, not to make definitive comparisons between arms. With 6 participants per arm, there is limited power to make comparisons between arms. Lu et. al. (2009) data estimates the difference in means of the ratio of CD4+ and CD8+ cells for patients treated with HIFU versus no HIFU to be 0.57, with standard deviations ranging from 0.27 to 0.40. These data provide an indication of the magnitude that could be detected in this study at baseline and 3 weeks, where it is assumed that the no HIFU participants in Lu et. al. are comparable to baseline measurements in our study. Using these data as a guideline, with n=6, we have 80% power to detect an effect size of 1.44 for the within-arm change in ratio of CD4+ and CD8+ cells at baseline and 3 weeks. Depending on the variability of the data, this is equivalent to detecting differences of 0.39 and 0.58, for assumed standard deviations of 0.27 and 0.40, respectively. The populations will include all intention to treat participants.

Safety stopping rules will be employed within each arm and will be judged by dose limiting toxicities (DLT). If the first two participants within an arm or 3 out of the 6 participants within an arm experience a DLT, that arm will be deemed too toxic and further accrual to that arm will be closed. This decision rule is based on Wald's sequential probability ratio test assuming lower and upper DLT proportions of 0.1 and 0.3, respectively, and type I and II error rates of 10%.

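### The only numeric stopping rule counts pembrolizumab toxicities, so severe harm attributed solely to HIFU has no pre-specified limit

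*Combined protocol and SAP*

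**What the plan says.** Section 8.2 gives the rule: "If the first two participants within an arm or 3 out of the 6 participants within an arm experience a DLT", the arm is judged too toxic and stops accruing. It is derived from Wald's sequential probability ratio test with DLT proportions of 0.1 and 0.3 and error rates of 10%. Section 8.1 refers to Section 7.2.10 for the event counted, and the definition there is limited to pembrolizumab: "A DLT of pembrolizumab is defined as an unacceptable, drug-related toxicity requiring permanent discontinuation", by reference to Table 4. Table 4 covers immune-related events; its note leaves other events to clinical practice. No other DLT definition appears.

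Both arms receive one HIFU session on day 15, which Table 3 labels experimental. Section 5.2.2 adds: "There is no dose modification for HIFU as it is only administered once in this protocol". On drug timing, Section 2.1 says: "Subjects randomized to Arm A will receive pembrolizumab administered IV every 3 weeks on days 22, 43, and 64". Arm B starts pembrolizumab on day 1.

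The only harm criterion among the early-termination reasons in Section 5.10 is: "Incidence or severity of adverse drug reaction in this or other studies indicates a potential health hazard to subjects". It carries no number.

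Other provisions do cover HIFU. Section 7.2.3 attributes events to the drug or the HIFU procedure. Serious events reach the sponsor within 24 hours (7.2.6). Unanticipated adverse device effects (UADEs) go to the IRB and FDA within 10 days and to the manufacturer within 5 (7.2.11.3 to 7.2.11.5). The DSMC meets monthly, and its remit includes all adverse events and the application of the stopping rules (10.7, 10.8).

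**The concern.** Preliminary safety of HIFU given with immunotherapy is a stated goal (2.1), and Section 4.4 says: "Our proposed study is the first study to combine HIFU and pembrolizumab in humans and safety is our secondary endpoint". The sponsor chose to set a numeric limit in advance, but that limit covers only the drug. Applied exactly, it would leave an arm open after six HIFU-only injuries in six participants, and a DSMC asked whether the rule had been met would have to answer no. Any decision to pause would then rest on judgement formed after the events. The protocol itself treats some HIFU risk as open: Section 5.2.1.2 says the risk to lung tissue is unknown, while chest-wall lesions may be treated.

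**Working it through.** **1. Does the plan's own boundary reproduce?** Inputs from Section 8.2: p0 = 0.1, p1 = 0.3, α = β = 0.1. The Wald upper boundary is crossed by x events in n when

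x·ln(p1/p0) + (n − x)·ln((1 − p1)/(1 − p0)) ≥ ln((1 − β)/α), which is 1.0986x − 0.2513(n − x) ≥ 2.1972.

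Solving for x gives 2.00 at n = 2, and 2.19, 2.37, 2.56 and 2.74 at n = 3 to 6. So 2 of 2 or 3 of 6 is right. The issue is what the rule counts.

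**2. How does the written rule behave?** For a per-participant event probability q,

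P(close) = P(X ≥ 3 of 6) + q²(1 − q)⁴,

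where the second term is two events in the first two participants and none after. At q = 0.1 this is 0.0158 + 0.0066 = 0.0224; at q = 0.3 it is 0.277. The HIFU-only rate h does not enter. With no drug DLTs the probability is 0 at any h.

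**3. What if HIFU events counted in the same rule?** Assumptions, none given by the documents as a combined-treatment rate: drug DLT rate d = 0.10 (the plan's lower proportion), HIFU severe-event rate h of 1.5% to 20%, independent events, six per arm. Then q = 1 − (1 − d)(1 − h). The column for closure before the sixth participant uses P(X ≥ 3 of 5) + q²(1 − q)³.

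| h | q | Arm closes, as written | Arm closes, HIFU counted | Of which before sixth participant |
|---|---|---|---|---|
| 1.5% | 0.1135 | 0.022 | 0.030 | 0.021 |
| 5% | 0.145 | 0.022 | 0.055 | 0.037 |
| 10% | 0.190 | 0.022 | 0.103 | 0.070 |
| 20% | 0.280 | 0.022 | 0.241 | 0.167 |

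About 30% of closures come only at the sixth participant, when the arm has reached its target of six; some accrual then remains only if the maximum of 15 is used. The chance that at least one arm closes, 1 − (1 − P)², goes from 0.044 to 0.060 at h = 1.5% and 0.194 at h = 10%.

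**4. Does a per-arm count suit HIFU?** Only partly. With no drug DLTs and h = 20%, q = 0.20 and a given arm closes with probability 0.115. Both arms receive the same procedure, so a pooled count uses all the information. P(X ≥ 3 of 12), HIFU events only, is 0.001, 0.020, 0.111 and 0.442 at h = 1.5%, 5%, 10% and 20%.

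**5. What do the documents say about h?** Section 4.2.2 reports no serious events in more than 200 patients. Taking 0 of 200, the one-sided 95% upper limit is 1 − 0.05^(1/200) = 1.5%. Section 4.4 adds: "Based on our experience at UVA (n=20) there has been no evidence of grade 4 toxicities in patients who received HIFU". Zero of 20 gives 1 − 0.05^(1/20) = 13.9%, but for grade 4 only.

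**The case against.** The strongest reply is that HIFU harm is already well watched. At 12 participants in 24 months, about one enters every two months, so monthly DSMC review of all adverse events permits case-by-case judgement, arguably sooner than a count of 3 in 6 would act. The procedure is given once, with limits on skin, rib and implant distance, beam direction and ablated volume. Besides the record above, Section 4.2.5 describes 42 fibroadenoma patients who tolerated treatment well, with skin irritation and erythema in 36% of cases that had resolved by one month. All of this stands and lowers the urgency. It does not supply a limit: the same oversight covers pembrolizumab, for which the sponsor still set one.

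Four stronger readings are tempting and are not supported.

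- That HIFU harm goes unmonitored. The reporting and DSMC provisions contradict this.
- That toxicity of the combination cannot count. It can, if attributed to pembrolizumab and meeting Table 4; the gap is harm attributed solely to HIFU.
- That the novelty of the combination makes the HIFU record irrelevant. For HIFU injury in Arm A before any drug, HIFU-alone experience is the right comparator.
- That 13.9% is a plausible severe-event rate. It is an upper limit for grade 4, and says nothing about grade 3 or higher. Grade 4 means life-threatening, which is a seriousness criterion in Section 7.2.2, so the 1.5% limit on serious events is already tighter.

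Two objections to the remedy also stand: a per-arm count fits an intervention common to both arms poorly, and a bare grade 3 threshold could close an arm for expected, short-lived procedural effects. The fix allows for both.

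**Conclusion.** The concern holds as a fault in the rule's scope. The boundary is correctly derived, but the event definition excludes one of the two experimental interventions, and the Section 5.10 wording does not make up for it. The rule's closure probability stays at 0.022 (10% drug DLT rate) however harmful HIFU proves. Including HIFU would barely change it if the device is as safe as reported (0.030 at 1.5%) and would raise it to 0.241 at 20%. These figures rest on assumed HIFU rates, independence and six participants per arm; the finding about scope rests on the text alone. It should be corrected, but in a 12-participant pilot with active oversight it is not evidence that participants are unprotected.

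**What to change.** 1. **Section 7.2.10.** Add to the DLT any UADE, and any grade 3 or higher toxicity probably or definitely related (7.2.3) to HIFU or to the combination, excluding expected transient procedural effects that the sponsor's clinicians list from the device manual. *Probable* is the working threshold, because *definite* requires recurrence and HIFU is given once. Keep the 2 of 2 or 3 of 6 boundary, and state in Section 8.2 that 0.1 and 0.3 now refer to drug and HIFU events together. The sponsor should confirm those values: a 10% drug rate with a 5% HIFU rate already gives a combined 0.145.
2. **Section 5.10.** Extend the harm criterion to device- or procedure-related adverse events.
3. **Pooled trigger.** Pause accrual in both arms for DSMC review when HIFU-attributed events across arms reach a set count, for example 3 of 12. The sponsor may choose another count.
4. **Attribution.** Record HIFU attribution separately from drug attribution. Table 7 asks only about the Merck product, and the adverse event form is not in the documents, so check whether a HIFU field already exists.

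The cost is wording in Sections 7.2.10, 8.2 and 5.10, possibly one form field, and the extra closures tabulated above. A false pause from the pooled trigger is rare if HIFU is safe: 0.001 at a 1.5% rate and 0.020 at 5%.
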